1. STUDY OVERVIEW – PURPOSE AND BACKGROUND

Asthma, the most common pediatric chronic condition, is a serious problem for many adolescents.¹ In 2010, nearly 11% of adolescents (2.7 million) ages 12 through 17 years in the US reported current asthma.² This age cohort suffers greater asthma-related morbidity and mortality than younger children.^{3, 4} Asthma disproportionately affects inner-city youth, where asthma severity has increased and achieving optimum asthma control has been elusive.⁵ Several factors including poor socioeconomic conditions, life stresses, and environmental triggers have been found to be associated with poorly controlled asthma in inner-city children.⁵ Programs targeting asthma in inner-city children have primarily focused on the modification of environmental factors⁶ and addressing disparity in healthcare access.⁷ Serious adverse outcomes requiring hospitalization, intubations and cardiopulmonary resuscitation are more common in adolescents than in younger children.⁸ Moreover, asthma mortality among teens is approximately twice that of younger children.³ Asthma results in decreased quality of life due to poor sleep quality and limited activity.^{4, 9} The impact of asthma on daily activities is substantial: over 50% of teens with asthma reported some degree of activity limitations.^{9, 10}

Limited intervention efforts have been directed to address high inner-city asthma morbidity specifically in adolescents by promoting adequate self-management. In adolescents, peers have the greatest influence over behaviors and psychosocial well-being, even in those with chronic illness. Peer support can increase adherence to disease self-management.¹¹⁻¹³ Adolescents with asthma highly value support from peers with asthma.^{14, 15} Positive interactions between adolescents with asthma have been found to have positive impact on their asthma management,^{16, 17} and overall psychosocial well-being.^{13, 18, 19} Therefore, providing a context in which adolescents with asthma can interact with each other can be beneficial in implementing an asthma self-management program for this age group. Given the high prevalence, limited interventions and serious adverse outcomes of asthma and its impact on quality of life in adolescents, it is imperative to implement effective strategies to improve self-management and health outcomes in this population. Building on [name] (PI) previous efficacy trial, the overall goal of the proposed study is to evaluate the effectiveness and generalizability of PLASMA, peer-led asthma self management for adolescents, in improving asthma outcomes in inner-city adolescents from three metropolitan cities in the Northern, Eastern and Southern US with distinctive historical and cultural backgrounds. Multisite studies have been advocated as an effective approach to strengthening external validity as such studies afford the opportunity to assess the extent to which treatment effects are generalizable to different settings.²⁰⁻²² Ascertaining generalizability across sites is important as it guides future translation of study findings into policy and practice.²² This study will also determine long-term sustainability of PLASMA effects and estimate the economic impact of the intervention. This multi-site study is significant in that it will target the understudied population, inner-city adolescents with asthma in three cities in the US, who present serious challenges to optimum asthma management.

Specific study aims are:

- 1) To evaluate systematically the effectiveness of a peer-led asthma program in inner-city adolescents with persistent asthma.

Hypothesis: We hypothesize that: relative to the control group, the PLASMA group will report greater improvement over time in (H1) quality of life (primary outcome), and (H2) asthma knowledge, attitudes, outcome expectations, self-efficacy, self-management skills, and asthma control, FEV1 (exploratory outcomes). (H3) The post-PLASMA scores on outcome measures will be higher than pre-program scores from both treatment groups.

- 2) To examine the mediating effects of the secondary outcomes (knowledge, attitudes, outcome expectations, self-efficacy, self-management skills, asthma control, and FEV1) on the primary outcome (quality of life) of the intervention.
- 3) To examine the moderating effects of personal factors (e.g., age, sex, family support) on primary and secondary outcomes of the intervention.
- 4) To evaluate the effects of PLASMA on primary and exploratory outcomes in peer leaders (16-20 years).

Hypothesis: We hypothesize that the peer leaders (n=42) will report significant improvement in quality of life (primary outcome) and secondary outcomes (knowledge, attitudes, outcome expectations, self-efficacy, self-management skills, asthma control and FEV1) over the course of 15 months.

- 5) To determine the economic impact of the intervention. This aim will be accomplished by (5a) measuring the direct healthcare costs and total costs of the PLASMA program, as compared with the control group; (5b) performing net cost analyses for each type of costs; and (5c) estimating cost-effectiveness ratios of the PLASMA group compared with the control.

Hypothesis: We hypothesize that the direct and overall costs per participant in the PLASMA group will be less than costs per participant in the control group, or cost neutral.

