Aim 5: The costs of services received during visits to a physician's office, outpatient department, or ED will be estimated by taking the global relative value unit for each service CPT (Current Procedural Terminology) code multiplied by a standard conversion factor.⁶¹ Hospital charges will be converted to costs using department-specific cost-to-charge ratio.⁶² Medications and dosages prescribed will be captured; standard wholesale unit cost from the Pharmaceutical Red Book⁶³ will be used to estimate medication costs. To calculate lost productivity costs of a family with a sick teen, we will estimate total lost income related to each participant by multiplying total number of work hours missed by a parent's hourly wage. Program costs will be estimated from the actual time peer and adult leaders spent in carrying out the program multiplied by hourly earnings, costs of equipment/ supplies, and overhead costs; program time will not include staff time for research-related tasks. We will estimate the average program cost per participant by study group, and include this estimate as one component of direct healthcare costs. The

medical or general Consumer Price Index⁶⁴ will be used to inflation-adjust costs to current year prices.⁶⁴ For each teen at each time-point, we will calculate total direct costs, direct costs by major category (office visit, hospitalization), indirect lost-productivity costs, and total direct and indirect costs. For withdrawals from follow-up, we will impute missing utilization and cost data assuming a linear trend in use and cost given prior experiences, where we will estimate weighted least square regression on log-transformed cost and obtain smearing-retransformed predictions.⁶⁵ For PLASMA and control groups separately, we will calculate the cost difference between each time point and baseline for each teen, assuming (s)he received “standard care” before treatment. Cost differences for each group will be modeled against follow-up points and individual covariates to estimate the independent impacts of each program on costs relative to standard care.

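### Aim 5 allows a cost-neutral conclusion without a margin, and the plan specifies no between-arm cost comparison that could support it

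*Combined protocol and SAP*

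**What the plan says.** Section 1 sets Aim 5 in three parts: (5a) measure costs in PLASMA as against control; (5b) "performing net cost analyses for each type of costs"; and (5c) "estimating cost-effectiveness ratios of the PLASMA group compared with the control". The hypothesis is that PLASMA costs per participant "will be less than costs per participant in the control group, or cost neutral". Neither Section 1 nor Section 10.1 defines the words "or cost neutral" or gives a margin.

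Section 10.1, Aim 5, covers unit costs, inflation adjustment and imputation for withdrawals in detail. Average program cost is estimated by study group, and the plan will "include this estimate as one component of direct healthcare costs". On comparison it says: "For PLASMA and control groups separately, we will calculate the cost difference between each time point and baseline for each teen". Those differences are then modelled on follow-up point and individual covariates "to estimate the independent impacts of each program on costs relative to standard care".

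Section 10.1 gives no PLASMA-versus-control cost contrast, test, interval or decision criterion. The cost-effectiveness ratio of 5c does not reappear there, so its effect measure, interval method and treatment of dominance are unstated.

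**The concern.** A claim that one program is cheaper than or as cheap as another is in substance a non-inferiority claim on cost. It needs a between-arm estimate, a limit on how much extra cost still counts as neutral, and a rule tying the interval to that limit. The plan has none of the three. The described model looks at each arm against its own baseline, so trends common to both arms enter both estimates, and neither estimate alone answers a between-arm hypothesis.

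Without a rule, a wide interval that includes zero could be presented as neutrality. This matters because Section 7.2 offers the economic results to policy makers considering adoption and names payers as possible adopters.

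The 5c ratio has a related gap. If quality of life is its denominator, the result that the plan hopes for (better outcome, equal or lower cost) yields a zero or negative ratio, and the size of a negative ratio cannot be interpreted.

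**Working it through.** **Inputs from the documents (Section 2.1(a)).** 276 participants for 80% power at alpha 0.05 on quality of life; 27% attrition; 378 in total, 63 per group at each of three sites, so 3 × 63 = 189 per arm.

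**The plan's own figure.** 276 / (1 − 0.27) = 378.08, which agrees with the stated 378. Only this attrition step was reproduced. The 276 depends on site-level variance and other inputs that are not given, and nothing below relies on how it was derived. No sample size or power is stated for costs.

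**Assumptions.** The cost CV (SD divided by mean) is not in the documents; the range 1 to 3 is used. Two analysis sizes bracket the plan: 276 / 2 = 138 per arm, and all 189 per arm. The second treats imputed costs as fully observed and is therefore generous.

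**Precision.** With a common SD, SE / mean = CV × √(2/n). For n = 138, √(2/138) = 0.1204; for n = 189, √(2/189) = 0.1029. The 95% half-width is 1.96 times the SE.

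**Chance that a true excess d is non-significant** (two-sided 5%, d as a fraction of mean cost): Φ(1.96 − d/SE) − Φ(−1.96 − d/SE). Example for CV 1, n = 138, d = 0.30: d/SE = 2.49, and Φ(−0.53) = 0.30; the second term is negligible.

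| CV | n/arm | 95% half-width (% of mean cost) | Missed at +30% | Missed at +50% |
|---|---|---|---|---|
| 1 | 138 | 24% | 0.30 | 0.01 |
| 1.5 | 138 | 35% | 0.62 | 0.21 |
| 2 | 138 | 47% | 0.76 | 0.45 |
| 3 | 138 | 71% | 0.87 | 0.72 |
| 1 | 189 | 20% | 0.17 | 0.002 |
| 1.5 | 189 | 30% | 0.51 | 0.10 |
| 2 | 189 | 40% | 0.69 | 0.32 |
| 3 | 189 | 60% | 0.84 | 0.63 |

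**What a margin could achieve.** If the true difference is zero, the smallest excess that can be ruled out with 80% power (one-sided 0.025) is (1.96 + 0.84) × SE. With 138 per arm this is 34%, 51%, 67% and 101% of mean cost at CV 1, 1.5, 2 and 3. With 189 per arm it is 29%, 43%, 58% and 86%. A 30% margin would need 175, 393, 698 and 1,570 per arm.

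**Sign of the ratio.** Suppose that quality of life is the denominator, that its true effect is 2.80 SE (1.96 + 0.84, the 80% power point), and that the cost and effect estimates are independent. The estimated ratio is negative when the two differences have opposite signs. At zero cost difference this happens in 50% of samples. At a cost difference 1 SE below zero the probability is Φ(1)Φ(2.80) + Φ(−1)Φ(−2.80) = 0.8413 × 0.9974 + 0.1587 × 0.0026 = 0.84. Two opposite findings can share one value: −$300 with +3 points, and +$300 with −3 points, both give −100 per point.

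**The case against.** A reader might infer that any non-significant cost difference would confirm the hypothesis. The documents do not say so: they state no between-arm cost test and no rule for reading one. The tabulated probabilities describe an ordinary two-sample test that the plan never specifies. They show what would follow if such a test were used and its null result were read as neutrality.

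A reader might also infer that the ratio must be zero or negative whenever the Aim 5 hypothesis is true. That does not follow. The hypothesis concerns cost only; the sign also depends on effect, which is the separate hypothesis H1, and 5c names no denominator. Lower cost with lower effect satisfies Aim 5 and gives a positive, interpretable ratio. A negative ratio when PLASMA is cheaper and better is dominance, not an error. Nor would the two −$100 cases necessarily be confused, since 5a, 5b and Aim 1 should show the sign of each component.

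The figures are also open to challenge. Costs come mainly from Medicaid claims (Section 4.1) and are imputed for withdrawals, so more than 138 per arm may be analysed. A constant program cost per group raises the mean without adding variance, which lowers the CV, and covariate adjustment may improve precision. At the favourable end, CV 1 with 189 per arm, a 30% excess is missed 17% of the time and a 50% excess almost never.

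Finally, the two within-arm estimates could be subtracted to give a between-arm contrast, and 5a and 5b show that a comparison is intended. But the plan does not state that step, its interval or a criterion. These objections narrow the concern and widen its range; they do not supply the missing margin or comparison.

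**Conclusion.** The point stands in limited form. Aim 5 offers neutrality as a successful outcome, but the analysis as written cannot establish it: there is no margin, no stated between-arm cost estimand and no interval rule. Nothing in the plan prevents an imprecise null from being taken as support.

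The size of the risk depends on the assumed CV of 1 to 3 and on the number analysed. A true 30% cost excess would go undetected in about 30% to 87% of trials at 138 per arm, or 17% to 84% at 189 per arm. The ratio problem is conditional: it arises if H1 holds, cost is equal or lower, and quality of life is the denominator. The gap there is the missing effect measure and dominance rule, not the use of a ratio as such.

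Severity is minor. Aim 5 is not the primary aim and does not size the trial.

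**What to change.** In Section 10.1, make the PLASMA-minus-control difference in mean cost per teen the Aim 5 estimand, with a bootstrap 95% interval. State the reading rule:

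- conclude less costly only if the whole interval is below zero;
- conclude neutral only if the upper limit is below a maximum acceptable extra cost fixed before unblinding;
- otherwise report the result as inconclusive.

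If no margin can be agreed, delete the neutral alternative from the hypothesis and make Aim 5 estimation-only.

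For 5c, name the effect measure. Show the joint cost-effect distribution on the cost-effect plane, with incremental net benefit (willingness to pay × effect difference − cost difference) over a stated range of willingness to pay. Where PLASMA is cheaper and better, or dearer and worse, report dominance in words instead of a negative ratio.

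The cost is SAP wording and a bootstrap program, with no change to data collection. The downside is that an inconclusive verdict becomes more likely, which reflects the precision available at this sample size.

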2. CHARACTERISTICS OF STUDY POPULATION

2.1 Subject Characteristics

Asthma and its morbidity disproportionately affect minority children of low-income families in inner cities, where asthma severity has increased and poses serious challenges to achieving adequate asthma control.⁵ Disparate burdens of asthma and its adverse outcomes among minority children have been consistently documented in the past 20 years.^{4, 23-25} In 2010, asthma prevalence in black children under 18 years was twice that of white youths; children in families below the poverty threshold as defined by the US Census Bureau were 1.5 times more likely to report current asthma than those in families at or above 200% of the poverty line.² Compared with white youth, black inner-city children are 4 and 3 times more likely to have asthma-related ED visits and hospitalizations respectively.⁴ The three cities where the study will take place, Buffalo, NY; Baltimore MD; Memphis TN demonstrate high rates of pediatric asthma, high health care utilization and high morbidity and mortality rates, thus this study will take place in these cities that are most likely to benefit from a proposed intervention.

a) Number of Subjects:

A total of 378 adolescents (12-17 years) and 42 adolescent peer leaders (16-20 years) will be recruited for this study. The sample size (N=378) is based on the power analysis using a novel method developed by Roy et al.²⁶ for a 3-level hierarchical longitudinal design based on the program "RMASS." This method has the advantage of incorporating three levels from the sites and repeated-measures from each subject with random-effects of the time trends at both the subject- and site-level, which are assumed to be equivalent in terms of sampling proportions, number of groups and differential attrition rates over time. In this proposed study, quality of life, the primary outcome, was used to estimate the sample size. Using data from the previous study,²⁷ the longitudinal trajectories of quality of life and its treatment-by-time interactions based on subject-level randomization were modeled: the estimated treatment*time interaction coefficient was 0.6 units, estimated SDs for error was 15, and the random-slope was 1.76. These estimated values with a Type-I error rate (alpha) of .05 yielded a total sample size of 276 that would detect a

time trend over eight time points (T1-T8) between groups with a power of .80. This sample size was estimated on the assumption that the analyses use multi-site hierarchical 3-level linear mixed-effects models. In the earlier study, the attrition rate of the inner-city subsample (n=55) was 27% including those who failed to attend the camp program (n=13, 23%) and those lost to follow-up (n=2, 4%). To compensate for a possible attrition rate of 27%, the total sample size was increased to 378 (126 for each site; 63 each of two groups).

b) Gender and Age of Subjects:

Recruitment will not be limited on gender. Based on epidemiological data, we will focus on adolescents from 12-17 years of age for campers and 16-20 years of age for peer leaders.

Participants will be stratified by gender and age (younger 12-14 years, older 15-17 years), which emerged as influential covariates in the PI's earlier study. Within each of four blocks generated by each combination of these two covariates, each subject will be randomly assigned to either group using a computer-generated randomization table. Stratified randomization will ensure a similar number of subjects representing each block in the two treatment groups, balancing the influence of age and gender. Stratified randomization will be done separately for each site, and centrally coordinated and managed. Within the treatment group, participants will be assigned to subgroups based on their age [younger (12-14 years) and older groups (15-17)] to allow the study team to adjust the levels of difficulty/complexity of program content delivered at the camp. In doing so, we will attempt to enhance participants' understanding of the information covered in the program. In the previous study, we found no differences in study outcomes or camp satisfaction between gender-matched groups and co-ed groups, so subgroups will be gender-mixed.

c) Racial and Ethnic Origin:

Enrollment of participants will not be restricted to any racial or ethnic groups. By recruiting participants from three cities with high prevalence and incidence of pediatric asthma, (again based on epidemiological data) we anticipate the sample demographic to have a higher proportion of minority populations representative of the neighborhoods targeted (Buffalo, Baltimore and Memphis.)

d) Vulnerable Subjects:

This study will include inner city adolescents between ages 12-17 years. This study will evaluate the effectiveness and generalizability of the peer-led asthma self-management program in adolescents in three cities including Buffalo NY, Baltimore MD and Memphis TN. The intervention has proved effective for inner-city adolescents in Rochester, NY.

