4. METHODS AND STUDY PROCEDURES

4.1 Study Procedures and Assessments

Design: This study will use a two-group randomized controlled design implemented in three metropolitan cities: Buffalo, NY, Baltimore, MD, and Memphis, TN. The project coordinator and a research assistant in each city who are not involved in direct patient care of teens with asthma will be responsible for recruitment and consent process taking place in each site. Peer leaders will attend a three-day intense training session that will take place prior to camps, lead small-group instructional activities at a one-day camp (PLASMA group) and follow up their group members bimonthly for 15 months. Camp participants from each site (n=126) will be randomly assigned to the peer-led (PLASMA) group or the adult-led (control) group. Upon enrollment, participants will be stratified by gender and age (younger 12-14 years, older 15-17 years), and randomly assigned to either group within each of four blocks generated by the combination of gender and age strata. Each group will attend a separate day camp where an asthma self-management program will be implemented either by peer leaders (intervention) or healthcare professionals (control). After the camp, the intervention group will receive peer-leader contacts bimonthly for 14 months using phone calls or other communication technologies (e.g., emails, or short-message system (e.g., texting) of teens' choice. Adult instructors (healthcare professionals) will contact the control group bimonthly for 14 months using similar methods, but different contact topics.

Both groups (intervention and control – more details below) will provide data at enrollment (T1), 3 months later (T2), immediately following the camp (T3), and at 3-, 6-, 9-, 12-, and 15-months post-camp (T4-T8).

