Self-reported (standardized questionnaires) and physiological (PEFR and Spirometry) data collected longitudinally (21 months) will capture systematic and dynamic processes by which the program modifies adolescents' self-management behaviors and health outcomes. The long-term observation will also allow the investigators to examine the sustainability of the intervention. Inclusion of multiple cognitive factors (knowledge, attitude, self-efficacy, and outcome expectations) as mediators will allow us to demonstrate intricate interrelationships or mechanisms between the intervention and asthma outcomes including asthma control and quality of life in adolescents. This study will also systematically investigate the economic impact (e.g., healthcare utilization, prescription and indirect costs) of the intervention, which will offer invaluable data to policy makers who might consider adopting the intervention as a standard care for teens with asthma. Moreover, this multi-site study involving three cities representing the Northeastern, Eastern and Southern sections of the US will provide evidence of the generalizability of the intervention and its impacts, which could further accelerate the adoption and implementation of the program to address the serious health threats of asthma in inner-city adolescents and to contain economic costs to society.

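### Do the sample-size inputs in section 2.1a contradict the stated N = 276 at 80% power?

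*Combined protocol and SAP*

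**What the plan says.** Section 2.1 (a), Number of Subjects, describes a program for three-level longitudinal designs that allows "random-effects of the time trends at both the subject- and site-level" and for attrition. Its inputs are estimates from an earlier study: "the estimated treatment*time interaction coefficient was 0.6 units, estimated SDs for error was 15, and the random-slope was 1.76". With alpha .05 they "yielded a total sample size of 276 that would detect a" "time trend over eight time points (T1-T8) between groups with a power of .80". The section adds: "This sample size was estimated on the assumption that the analyses use multi-site hierarchical 3-level linear mixed-effects models". The 276 is then raised to 378 to allow for 27% attrition.

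Three other places matter.
- Section 1 states the primary hypothesis directionally: "the PLASMA group will report greater improvement over time in (H1) quality of life (primary outcome").
- Section 4.1 sets assessments "at enrollment (T1), 3 months later (T2), immediately following the camp (T3), and at 3-, 6-, 9-, 12-, and 15-months post-camp (T4-T8").
- Section 7.2 gives the span: "data collected longitudinally (21 months"). Eight assessments over 21 months are 3 months apart.

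Section 10.1 (Aim 1) analyses the outcome with a three-level mixed model that has a treatment effect and a treatment-by-time interaction.

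**The concern.** This is the trial's only power statement for its primary outcome, so a statistician will try to reproduce it. The obvious attempt takes 15 and 1.76 as standard deviations, two-sided alpha .05, and time in either visits or months. It fails on both scales, and by a wide margin for visits. The slope variance alone, 1.76² = 3.098, already needs about 270 subjects, which leaves almost nothing of the 276 for measurement error.

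If the stated .80 were really 0.40 or 0.74, the trial could miss the effect it was designed to find, and a null result could be wrongly read as evidence against the peer-led program.

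**Working it through.** **Inputs.** Section 2.1 (a): slope difference 0.6, error 15, random slope 1.76, alpha .05, power .80, eight time points. Sections 4.1 and 7.2: visits every 3 months from 0 to 21. Equal allocation within three sites.

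**Formula.** For two equal arms with complete data and separate group intercepts:
- V = error variance / SS(time) + slope variance
- N = 4 (z_alpha + 0.842)² V / 0.6²

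SS(time) is 42 in visits (0 to 7), 378 in months and 7098 in weeks (0 to 91 in steps of 13). The multiplier (z_alpha + 0.842)² is 7.849 two-sided and 6.183 one-sided. A site time trend shared by both arms cancels under within-site randomization.

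**The plan's attrition step.** 276/0.73 = 378.1 and 378 × 0.73 = 275.9. This agrees with 378.

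**Readings of the inputs.**

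| Error | Slope | Time unit | Sides | V | N | Power at 276 |
|---|---|---|---|---|---|---|
| SD 15 | SD 1.76 | visits | 2 | 225/42 + 3.098 = 8.455 | 737 | 0.40 |
| SD 15 | SD 1.76 | months | 2 | 225/378 + 3.098 = 3.693 | 322 | 0.74 |
| SD 15 | SD 1.76 | months | 1 | 3.693 | 254 | 0.83 |
| variance 15 | SD 1.76 | months | 2 | 15/378 + 3.098 = 3.137 | 273.6 | 0.80 |
| SD 15 | variance 1.76 | months | 2 | 225/378 + 1.76 = 2.355 | 205 | 0.90 |
| SD 15 | SD 1.76 | weeks | 2 | 225/7098 + 3.098 = 3.129 | 272.9 | 0.80 |

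**Which readings fit 276.**
- Error variance 15 in months: 273.6/6 = 45.6, rounded up to 46 per arm per site, gives 6 × 46 = 276 exactly.
- Weeks also come close, but 0.6 × 91 = 54.6 units at the last visit is implausible.
- The 254 and 205 rows lie below 276 before any site variation. Adding tau²/3 to the variance of the slope difference, where tau is an assumed between-site SD of the treatment slope, brings them to 276 at about 0.12 and 0.19 per month respectively. Neither tau is printed in the protocol.

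A near match does not identify the reading, because the slope variance of 3.098 alone gives 270.

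**Power with all 378 enrolled.** Section 10.1 plans likelihood-based mixed models, so partial follow-up contributes. Take both values as SDs, months, two-sided, with independent intercept and slope (intercept variance 50 to 1000, assumed):
- Dropout rising linearly to 27% needs N of 376 to 378, so 378 gives power 0.80.
- Early dropout, with 23% leaving after T2 (the camp no-show rate in section 2.1 (a)) and 4% after T5 (timing assumed), gives 0.76.
- In visits, the same two patterns give only 0.41 to 0.44.

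**The case for a change.** The strongest case for action is that the plural label most naturally covers both values, two-sided testing is the usual default, and visits or months are the obvious scales for this schedule. On that reading 276 does not follow from the inputs. Each route back to 276 needs a changed label, an implausible unit or an unprinted setting. In the separate-intercept model, site-by-treatment variation or dropout only raises N. That several incompatible readings fit the same figure shows how loosely the paragraph is specified.

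Much of this stands. The arithmetic is right under its stated conditions. The time unit, sidedness, level of the random slope, and site and attrition settings are indeed absent.

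The step from there to an error does not stand. The sentence can also be read with the SD label attached to the error term alone, which in months gives 205. The coefficient and slope come from a previous study whose time scale is not given, so this trial's visit spacing does not fix their unit. The per-visit reading, which produces the alarming 737 and 0.40, has no support in the text beyond being possible. A two-level formula without dropout also cannot overturn a three-level program whose settings are unknown. The check shows that the figure cannot be verified, not that it is wrong.

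**Conclusion.** The concern does not call for a change. Section 2.1 (a) omits details needed to reproduce 276, but nothing in the documents shows that 276 or .80 is wrong. Power at 276 runs from 0.40 (both as SDs, visits, two-sided) through 0.74 (months) to 0.80 (error variance 15, months) and 0.90 (slope variance 1.76, months). The documents do not say which applies. On the monthly SD reading, 378 enrolled with partial follow-up gives about 0.76 to 0.80, so any shortfall there is small. The per-visit reading would be a real shortfall, but it rests on a unit that no passage supplies.

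Writing down the unit, sidedness, labels, level and program settings would help a later reader check the figure. It would not alter enrolment, which stays at 378, or the mixed-model analysis, which estimates its own variances. A null result should be read from the confidence interval for the slope difference, and the planning inputs play no part in that. This is missing detail, possibly with a mislabelled variance.

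These figures rest on the two-level approximation, equal spacing of 3 months, and the assumed intercept variances, dropout timing and site SDs stated above.
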